❖ Independent variable: In this study, independent variable is defined as to have been or not to have been vaccinated with Bexsero.

To classify a child as vaccinated, he must have finished the vaccination regimen according to his age as we can see in the table below adapted from the technical file of Bexsero. Booster doses are not required to consider a child as correctly vaccinated.

Age group	Primary	Dose interval	Booster dose
	immunisation		
From 2 months to	3 doses of 0.5 ml	At least 1 month.	1 dose between 12
5 months	each one, starting		and 15 months.
	the first dose at 2		Never after 24
	months or later.		months.
From 6 months to	2 doses of 0.5 ml	At least 2 months.	1 dose during the
11 months	each one.		second year of life
			with a minimum
			dose interval of 2
			months since the
			primary
			immunisation.
From 11 months to	2 doses of 0.5 ml	At least 2 months.	1 dose with a dose
23 months	each one.		interval from 12 to
			23 months since the

			primary immunisation.
From 2 years to 10 years	2 doses of 0.5 ml each one.	At least 2 months.	Not established.
11 years or more	2 doses of 0.5 ml each one.	At least 1 month.	Not established.

Vaccination's state will be collected checking the code corresponding to Bexsero: **P00157**.

❖ Outcome variable: In that case, outcome variable for the primary objective is the number of cases of IMD. As it has been said in the introduction we mainly consider IMD as:

Meningitis: it is defined as an inflammatory process of the leptomeningeal membranes who overcoat the CNS.

Information about diagnosis of meningococcal meningitis is codified in hospital registers as **036.0**.

Sepsis: it is defined by the presence of systemic inflammatory response syndrome due to an infection (suspected or confirmed). That syndrome is characterised by the presence of 2 of the following:

- Axillary temperature >38°C or <35,5°C. *
- Tachycardia: cardiac frequency >2 Standard Deviations according to the age of the patient without medication or external or painful stimuli.
- Tachypnea: respiratory frequency > 2 Standard Deviations according to the age of the patient.
- White cell count elevated or diminished for the age of the patient or >10% of immature neutrophils. *

Information about diagnosis of sepsis is codified in hospital registers as **036.2** (meningococcal sepsis) and **036.3** (Sd. Waterhouse-Friedrichsen).

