- Adverse reactions registered: it is a dichotomous qualitative variable. It is registered as presence of adverse reaction associated with vaccination (Yes or No). It will be described by percentages.

Covariables:

- Sex: it is a dichotomous qualitative variable, described by percentages.
- Age: it is a discrete quantitative variable, defined by mean and standard deviation if it is normally distributed or by median and quartiles in case of non-normal distribution. It will be expressed a confidence interval of 95%.
- Ethnicity: it is a categorical qualitative variable, described by percentages.
- Socioeconomical status: it is a discrete quantitative variable and it will be described by mean and standard deviation if it is normally distributed or by median and quartiles in case of non-normal distribution. It will be expressed a confidence interval of 95%.

BIVARIANT ANALYSIS

To compare the independent variable, which is categorical qualitative, with the main dependent variable, which is discrete quantitative, we will use the Mann-Withney test.

To compare the independent variable with the secondary dependent variable, which are both categorical qualitative we will use the Chi ² test.

To compare qualitative variables between them we will use Chi² test, and to compare quantitative variables between them the Pearson rank or Spearman rank, depending if they are normally distributed or not.

MULTIVARIANT ANALYSIS

It will be used a Cox model adjusted for Propensity Score punctuation, for confounding variables.

ETHICAL AND LEGAL CONSIDERATIONS

The present protocol will be presented for its approval to the Comité d'Ètica i Investigació Clínica (CEIC) de l'Institut d'Investigació i Recerca en Atenció Primària Jordi Gol.

Moreover, we will present that protocol to the Agencia Española del Medicamento y Producto Sanitario (AEMPS) since this is a post-authorisation observational study and it has to be classified.

Once we have obtained the Ethics Commitee's approval and the AEMPS's classification, we present the protocol to the Departament de Salut de Catalunya- Subdirecció General de Recerca i Innovació en Salut, since we are using a vaccine which is a drug.

Finally, in a voluntary way, we will register that protocol to the European Network of Centres for Pharmacoepidemiology and Pharmacovigilance (ENCePP) in order to avoid a possible publication bias.

The project will guarantee that the following considerations and legislations are respected:

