- World Medical Association -Declaration of Helsinki: Ethical Principles for Medical Reasearch Involving Human Subjects from 1964.
- ❖ Spanish Law: "Ley 14/2007 de Investigación Biomédica"
- Real Decreto 1090/2015- Regulación de los Ensayos Clínicos con medicamentos, Comités de Ética de Investigación con medicamentos y el Registro Español de Estudios Clínicos.
- Orden SAS/3470 de 2009- Directrices sobre Estudios Post- Autorización de Tipo Observacional para Medicamentos de Uso Humano.

Because we are using a preexisting database as SIDIAP where all information is anonymised and codified it is no necessary ask for Informed Consent, according with current legislation:

- Ley Orgánica 41 de 2002- Autonomia del Paciente y de Derechos y Obligaciones en Materia de Información y Documentación Clínica.
- Ley Orgánica 15 de 1999- Protección de Datos de Carácter Personal.

The investigators have no conflict of interests.

STRENGTHS AND LIMITATIONS

As any other study, certain limitations exist. Those limitations can be related with the study design, its associated biases and with the sample's obtention.

STUDY DESIGN

Although Clinical Trial is the best design for assess the effectiveness of a preventive measure, that design would entail several difficulties, which would seriously affect the results obtained and its validity.

The main reason to not perform a Clinical Trial is that given the low incidence of IMD at current moment, it would be necessary to enrol a lot of participants in the study and also a long follow-up period to obtain IMD cases and see if the vaccine is effective or not in its prevention.

Therefore, to carry out a Clinical Trial a big inversion of time and resources will be needed, so it would not be feasible right now.

To solve all that issues it has been choosen a cohort study and a data source as SIDIAP. That data source allows the obtention of sufficient participants, and the design allows its follow-up during an adequate period of time, making feasible the study even the current epidemiological situation.

BIASES

Observational studies have an important limitation, because we cannot randomly assign participants to one group or another.

That fact causes that differences observed may be due to the existence of confounding variables.

For that reason, in this study it is very important controlling that confounding variables. Hence, they are collected during data collection phase and controlled with a multivariant anlysis.

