The analysis we will perform will be adjusted with the Propensity Score (PS).

PS is a useful tool that helps to know if we are comparing two groups that are similar between them except for the independent variable we are studying.

So, we establish *a priori* which variables can be confounding and, according with PS punctuation, we will know if two groups are homogeneus and the results that we are observing are due to the measure we are assessing.

SAMPLE

The big sample size required to carry out the study could be a limitation, however because we obtain information through SIDIAP database, which includes a high part of population in Catalunya, we can easily access to all information required as well as obtain a sufficient number of participants in the study.

In fact, using a big sample provides a high external validity to the results since the sample we are studying is highly representative from target population.

WORK PLAN

In this section we are going to describe the phases of the study as well as which activities will include, who is going to carry out every phase and how long is going to take each one.

The study will last 7 years and 4 months and it will be structured in 4 phases.

PHASE 1- Coordination & Development of the protocol (6 months)

- ❖ Activity 1: Meeting to define who is going to participate in the investigation and assigning functions to every member of the research team. All members participate.
 (M1)
- ❖ Activity 2: Defining an Hypothesis, Objectives and Variables for its collection from SIDIAP database. All members participate. (M1-M2)
- ❖ Activity 3: Bibliography research. Three members of the research team. (M1- M2)
- ❖ Activity 4: Pilot test of data extraction, problems detection and correction. Two members of the research team. (M3)
- ❖ Activity 5: Elaboration of final protocol. All members participate. (M3-M4)
- Activity 6: Sending the protocol to the Ethics Committee and to AEMPS for its aproval and classification. Main investigator & another member of the research team. (M4-M6)
- ❖ Activity 7: Register the protocol into ENCePP. Main investigator. (M6)
- ❖ Activity 8: Design a database for the study. One member of the research team. (M3-M6)

PHASE 2- Participants recruitment & Data collection (6 years)

- ❖ Activity 9: Participants recruitment will last 1 year. (M6-M18)
- ❖ Activity 10: Follow- up for every subject included in the study for 5 years. (M6-M78)

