- ❖ Activity 11: Data collection. Information regarding variables and covariables for the study will be collected and introduced in our study database. Information will be depurated and reviewed before being introduced into our database. All members participate. (M6-M78)

PHASE 3- Statistical analysis & interpretation of the results (5 months)

- ❖ Activity 12: Data obtained will be analyzed by statistician. One member of the research team. (M78-M80)
- ❖ Activity 13: Investigators will discuss the results obtained, after their statistical analysis. All members participate. (M80-M82)

PHASE 4- Final report elaboration & Publication of the results (5 months)

- ❖ Activity 14: Final report writting. Main investigator. (M83-M85)
- ❖ Activity 15: Final report dissemination: Submitt the results to the principal medical journals to be published. Main investigator. (M85-M87)

STUDY CHRONOGRAM

		2017	2018		2019	2020	2021	2022	2023	2024
PHASE 1- Coordination & l	Devel	opment of	the protocol							'
Act 1- Coordination meeting										
Act 2- Hypothesis, Objectives & Variables										
Act 3- Bibliography research										
Act 4- Pilot test										
Act 5- Final protocol elaboration										
Act 6- Protocol approval										
Act 7- Protocol register										
Act 8- Database design										
PHASE 2- Participants rec	ruitm	ent & Data	collection				'			
Act 9- Participants recruitment										
Act 10 – Follow- up										
Act 11 – Data Collection										
PHASE 3- Statistical analys	sis & i	nterpretat	ion of the res	ults						
Act 12- Statistical analysis										
Act 13- Discussion										
PHASE 4- Final report elab	orati	on & Public	cation of the	results						
Act 14- Final report elaboration										
Act 15- Publication of the results										

BUDGET

This study is observational and certain aspects of daily practice are not modified, such as indications or recommendations for vaccination with Bexsero given by paediatricians and the decision of vaccinate or not vaccinate made by parents, Bexsero's administration place, number of doses, children's visits schedule or Primary or Hospitalary attention in IMD cases (complementary tests performed, treatments administrated).

For that reasons, the cost of Bexsero is not included in the budget. Moreover, paediatricians and nurses who are going to administrate Bexsero and make the visits to the participants, making the recruitment and follow-up will not receive a special compensation.

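### The protocol promises propensity-score adjustment, but the methods it names do not deliver it for the Yes/No adverse-reaction outcome, where the only test named is a crude chi-square

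*Protocol*

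**What the plan says.** The secondary hypothesis (Protocol, Hypothesis) is that children given Bexsero on top of routine vaccines have a higher proportion of adverse reactions than children given routine vaccines only. The secondary objective is the matching comparison between cohorts.

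In Variable description and statistical analysis, the univariate part defines the outcome: "It is registered as presence of adverse reaction associated with vaccination (Yes or No"), to be summarised by percentages. Study variables says that reactions are identified by a record code (T66). It gives no onset date, risk window or time origin for them.

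The bivariate part names the test: "To compare the independent variable with the secondary dependent variable, which are both categorical qualitative we will use the Chi ² test".

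The multivariable part is a single sentence: "It will be used a Cox model adjusted for Propensity Score punctuation, for confounding variables". It does not say which outcome is modelled.

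Strengths and limitations, under Biases, says of the lack of randomisation: "That fact causes that differences observed may be due to the existence of confounding variables". On the confounders it says: "Hence, they are collected during data collection phase and controlled with a multivariant anlysis". It then adds: "The analysis we will perform will be adjusted with the Propensity Score (PS"). Neither promise is restricted to IMD. The covariates to be controlled (Study variables, Covariables) are sex, age, ethnicity and socioeconomic status by the MEDEA index.

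**The concern.** Who receives Bexsero is not set by the study. The Budget section lists among the aspects of daily practice left unchanged the "indications or recommendations for vaccination with Bexsero given by paediatricians and the decision of vaccinate or not vaccinate made by parents". The protocol itself names four characteristics that may influence whether a child is vaccinated. If any of them also affects how often a reaction is recorded, the crude percentages in the two cohorts differ for reasons unrelated to the vaccine.

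For this outcome the protocol names one test, and it is crude. The one adjusted model it names does not fit the variable as defined. An analyst who follows the methods section literally can finish the secondary hypothesis at the chi-square.

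The stakes are stated in Impact to the National Health System: an association between Bexsero and more reactions would alter current recommendations. A difference in cohort make-up could be taken for such an association, or could conceal a real one.

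**Working it through.** **Step 1. Match promise to method.** No figure in the protocol depends on this point, so the main check is to set the sections side by side.

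| | IMD | Adverse reactions |
|---|---|---|
| Outcome as defined | number of cases over a 5-year follow-up | Yes/No per child |
| Crude test named | Mann-Whitney | chi-square |
| Adjusted model named | Cox with propensity score (no outcome stated) | the same sentence, if it applies |
| Event time | not spelled out, but follow-up is for new cases over 5 years | none defined |
| General promise of adjustment | applies | applies |

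No logistic, log-binomial or Poisson model is named anywhere, and no matching, weighting or stratification on the propensity score. The promise reaches the last column, but no method fitted to a Yes/No variable does.

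**Step 2. Could a crude chi-square mislead here?** This is an illustration only. From the protocol: cohort sizes 14,108 and 70,540. Assumed, because the protocol gives none of it: two age groups at entry (infants, later entrants), 6 and 2 routine vaccination visits respectively, risk q of a recorded reaction per visit, and the share of infants f in each cohort. There is no Bexsero effect.

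- Risk of at least one reaction: r = 1 − (1 − q)^k, where k is the number of visits.
- Crude risk in a cohort: f × r(infant) + (1 − f) × r(later).
- z = difference / √[p(1 − p)(1/14,108 + 1/70,540)], with p the pooled risk. The rejection rate uses the unpooled variance for the distribution of the difference.

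Worked case, q = 2%: r(infant) = 1 − 0.98^6 = 11.42% and r(later) = 1 − 0.98^2 = 3.96%.

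- Cohort 1 with 25% infants: 0.25 × 11.42 + 0.75 × 3.96 = 5.82%.
- Cohort 2 with 15% infants: 0.15 × 11.42 + 0.85 × 3.96 = 5.08%.
- Pooled p = (5.82 + 5 × 5.08)/6 = 5.20%, standard error 0.205 percentage points, z = 3.64, rejection 0.95.

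Rejection rate of the nominal 5% test, no vaccine effect:

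| Infants, cohort 1 vs 2 | q = 0.1% | q = 0.5% | q = 2% | crude risk ratio |
|---|---|---|---|---|
| 15% vs 15% | 0.05 | 0.05 | 0.05 | 1.00 |
| 17% vs 15% | 0.06 | 0.07 | 0.12 | 1.03 |
| 20% vs 15% | 0.08 | 0.16 | 0.45 | about 1.07 |
| 25% vs 15% | 0.15 | 0.46 | 0.95 | about 1.15 |
| 5% vs 15% | 0.12 | 0.48 | 0.97 | about 0.85 |

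With 4 and 2 visits instead of 6 and 2, the 25% vs 15% row becomes 0.08, 0.18 and 0.50.

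**Step 3. Could it hide a real difference?** Assume that in cohort 1 Bexsero is given at 3 of an infant's 6 routine visits and at both of a later entrant's, and raises the risk at those visits by a factor of 1.2.

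- Equal age mix: risk ratio 1.16, with rejection 0.52 (q = 0.5%) and 0.98 (q = 2%).
- 5% vs 15% infants: crude ratio 1.01 against 1.18 to 1.19 standardised to cohort 1's age mix, with rejection 0.05 to 0.06.

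**Step 4. Does the proposed remedy behave?** In simulations without a vaccine effect (24 scenarios of the Step 2 kind, 2,000 runs each), adjustment for age band gave rejection rates of 0.038 to 0.058 with logistic regression and 0.040 to 0.058 with modified Poisson regression. Age was the only confounder in those data, so this confirms that the models work at these sample sizes and no more.

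**The case against.** The strongest reply is that adjustment has already been promised without restriction, that the chi-square stands in the bivariate step just as a crude Mann-Whitney test does for IMD, and that the regression family for a secondary outcome can be left to a statistical analysis plan. Much of this stands. A reader might infer that the protocol ignores confounding for reactions, or makes the chi-square the final word. The text supports neither reading, because its general promise covers reactions in intent. What remains is that the protocol is not silent: it names a test for this outcome and names one adjusted model, and the two together do not deliver the promise. A later analysis plan that kept to the protocol would inherit that.

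A second reply is that Cox regression is not impossible here. It could be fitted to time to first coded reaction if record dates were used. That is correct, and the point should not be read as saying otherwise. The protocol, however, defines no such time, and its hypothesis concerns a proportion.

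A third temptation is to argue that age must confound because the primary series has three Bexsero doses in the youngest infants and two later. That does not follow. The schedule applies to cohort 1 only and is part of the exposure, so it may modify the effect of Bexsero but does not show a difference in background reaction risk between the cohorts.

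Finally, the illustration is open to the charge that its inputs are chosen. They are assumed throughout, and rejection rates near 0.95 need both a ten-point imbalance in infants and a 2% risk per visit. With a two-point imbalance the distortion is small.

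**Conclusion.** The point holds, as a mismatch between a stated intention and the stated methods for a secondary outcome. The only test named for adverse reactions is crude, and the only adjusted model names no outcome and lacks a defined event time for them. The comparison of non-randomised cohorts could therefore be left unadjusted, against the protocol's own emphasis on controlling confounding.

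No size can be attached to the resulting bias. The assumed inputs give anything from no distortion to a near-certain false difference in either direction, or a real difference largely hidden. A reader might take the 0.95 or 0.97 as the expected error rate. The documents do not support that, since they give no visit counts, reaction risks or age mix by cohort. Nor do they show that any of the four covariates is in fact unbalanced.

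The change is worth making but moderate in weight. The outcome is secondary, and the protocol leaves any causal claim to later research. Confidence is medium.

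**What to change.** In Variable description and statistical analysis:

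- Keep the chi-square as the crude, descriptive comparison of percentages.
- Base the conclusion on adverse reactions on a propensity-score- or covariate-adjusted model for a binary outcome: logistic, log-binomial or modified Poisson regression, with age at entry, sex, ethnicity and MEDEA index. Report the adjusted odds or risk ratio with its 95% CI. Because the hypothesis concerns a proportion, a risk ratio is the closer match.
- State that the Cox model applies to IMD.

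This takes a few sentences. The covariates are already planned for collection, so no new data are needed. The cost is slightly more analysis and a summary less simple than a difference in percentages. The adjustment deals only with the listed covariates; other differences between vaccinating and non-vaccinating families would remain.

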ANNEX 2: INCIDENCE RATES OF IMD DUE TO SEROGROUP B

From: Asociación Española de Pediatria, Asociación Española de Vacunologia. Vacuna frente a la enfermedad meningocócica invasora por serogrupo B. Información para profesionales sanitarios. Madrid. Ministerio de Sanidad, Servicios Sociales e Igualdad. 2016.

ANNEX 3: Epidemiology of IMD in European Countries in 2011.

	Casos totales de EMI confirmados en 2011	Casos de EMI por 100.000 personas/año	Casos totales de EMI por MenB en 2011	Casos de EMI por MenB por 100.000 personas/año
Alemania	370	0,45	219	0,3
Austria	49	0,58	15	0,2
Bélgica	111	-	83	0,8
Chequia	63	0,60	34	0,3
Dinamarca	72	1,30	27	0,5
Eslovaquia	21	0,39	11	0,2
Eslovenia	13	0,63	9	0,4
Estonia	7	0,52	5	0,4
España	431	0,93	304	0,7
Finlandia	34	0,63	19	0,4
Francia	563	0,87	395	0,6
Grecia	52	0,46	43	0,4
Holanda	106	0,64	66	0,4
Hungría	67	0,68	28	0,3
Irlanda	89	1,95	84	1,9
Italia	152	0,25	75	0,1
Letonia	2	1,38	1	0,09
Lituania	42	0,10	28	0,9
Luxemburgo	2	0,39	-	_
Malta	6	1,44	2	0,5
Noruega	37	0,75	10	0,2
Reino Unido	1036	1,67	837	1,3
Polonia	282	0,73	152	0,4
Portugal	56	0,54	49	0,3
Rumania	68	0,32	29	0,1
Suecia	68	0,72	15	0,2
Total	3776	0,75	2551	0,5

ECDC: European Centre for Disease Prevention and Control; EMI: enfermedad meningocócica invasora; MenB: meningococo serogrupo B.

Figure from: Moreno-Pérez D, Álvarez García FJ, Arístegui Fernández J, Cilleruelo Ortega MJ, Corretger Rauet JM, García Sánchez N, et al. Vacunación frente al meningococo B. Posicionamiento del Comité Asesor de Vacunas de la Asociación Española de Pediatria. An Pediatr. 2015;82(3):198.e1-198.e9.

ANNEX 4: LUMBAR PUNCTURE CONTRAINDICATIONS

CONTRAINDICACIONES DE PUNCIÓN LUMBAR

- Inestabilidad cardiorespiratoria.
- Diátesis hemorrágica: CID, trombocitopenia con plaquetas < 50 000 o un INR >1,4.
- Aumento de la presión intracraneal detectado por coma, pupilas anormales, postura, parálisis del III o VI PC, papiledema, bradicardia, hipertensión o alteraciones del patrón respiratorio.
- Afectación cutánea de la zona donde se practica la punción lumbar.

Figure from: Tellez Gonzalez C, Reyes Dominguez S. Meningitis Bacteriana Aguda. Sociedad Española de Cuidados Intensivos Pediátricos (SECIP); 2010.
